### **Estimation of costs, and cost-effectiveness:**

We will estimate the total Investigator, research staff, and clinic staff time involved in data gathering in Phase 1, and for training, implementation, supervision, and for each type of solution delivered to patients in Phase 2. This will be based on the time spent on different study related activities, recorded by research and clinic staff in their time logs. The total effort for public health evaluation and intervention implementation for health facility staff and research staff will be estimated from these total times. The average salaries of the different cadres of health facility workers will be used to value these activities. From this we will estimate total costs for each activity, and from the numbers of index cases and contacts derive an average cost per index case, or per contact. The primary cost-effectiveness measure will be the total cost of all Phase 2 activities *per additional contact who starts LTBI therapy*. Additional will be calculated based on the difference in proportion starting LTBI therapy between the pre- and post-intervention periods.

As well we will tabulate all diagnostic tests, visits and drugs related to contact management. Costs for these health care activities will be estimated using the WHO cost indices as described above. Patient costs will be ascertained in a sample of patients based upon a short interviewer-administered questionnaire regarding time taken for the various steps of the contact investigation and management as well as their out of pocket expenses related to travel, food etc. Incremental health system costs will be expressed per additional contact initiating LTBI (primary outcome), and per additional active TB case detected, and per contact completing LTBI therapy (secondary outcomes) as measures of cost-effectiveness.

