### **Secondary:**

- 1) To evaluate the effectiveness of the standardized public health evaluation and solution packages at improving: the proportion completing LTBI treatment, of those who start.
- 2) To evaluate the health system costs associated with current management of active TB, contact investigation, and latent TB diagnosis and treatment as well as the costs associated with the evaluation and implementation of appropriate solutions – including staff time and other resources used – in order to assess their feasibility, and cost-effectiveness.
- 3) To evaluate the sustained effect of this complex intervention for one year after the end of the randomized trial
- 4) To evaluate the costs, and impact of a stream-lined Phase 1 and 2 – administered to control sites, after the 18 month trial.

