### **Rationale for study design**

The study is designed as a pragmatic public health intervention study in that the intervention package will be tailored to the problems identified from the standardized public health evaluation in that country.

The specific problems and changes required will not be exactly the same in all sites, raising potential concerns over generalizability. **However the intervention being tested is the approach – a standardized public health evaluation and analysis, with identification of problems (barriers), and appropriate solutions.** The initial evaluation will utilize standardized questionnaires, and data gathering to facilitate replication in other settings. We have reduced the variability of the final solutions package by limiting the budget allocated for these solutions. This type of public health intervention has been used successfully in other cluster randomized trials - training hospital staff in Senegal and Mali to conduct maternal mortality review resulted in reduced maternal mortality, and facilitation of women's group meetings in Nepal lead to improved birth outcomes. In both studies the actual solutions that were implemented were site-specific; it was the process to identify problems that was standardized.

The choice of LTBI treatment regimen by the primary providers will follow local treatment guidelines. This for several reasons: i) The primary objective of the trial is to evaluate interventions up to treatment initiation – which will not be affected by the treatment selected; ii) The current standard in most countries remains INH for 6 or 9 months; iii) The 4RIF vs 9INH trial will only be finished in early 2017, so findings from that RCT will not affect practise until close to the end of this study.

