## **DATA GATHERING:**

### **Study Outcomes:**

Based on the primary study objective, the key data to be collected prospectively after the trial begins is the number of patients diagnosed with microbiologically confirmed Pulmonary TB (index cases) (also will collect number of not confirmed pulmonary and not pulmonary), the number of identified household contacts of these index cases with confirmed pulmonary TB, and the number of household contacts who started LTBI therapy. Note that the number who actually complete therapy is not required as this is a secondary outcome that occurs later and data will be collected retrospectively. The primary study outcomes of number of index cases, number of household contacts identified and the number of household contacts starting LTBI therapy must be measured every month at all health facilities (Intervention and Control) throughout the trial. Outcomes will be recorded using a standardized form. More detail on data sources and how to ascertain study outcomes is provided below.

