**DATA ANALYSIS FOR PHASE 2****Contact investigation outcomes:**

Among the household contacts, the following outcomes will be measured

1. Contacts identified.
2. **Started LTBI therapy** (primary outcome)
3. Completed LTBI therapy (secondary outcome)

The primary outcome will be the proportion of identified contacts who start LTBI therapy – in the final 6 months of the trial (to account for delayed impact of this complex intervention). If we find that more than 20% of contacts are diagnosed to have active TB, which would be far in excess of published experience, then we would investigate if this reflected over-diagnosis.

Our analysis will be performed at the level of the individual, but will account for correlation between subjects from the same centre. Population averaged logistic regression with an identity link estimated via generalized estimating equations (GEE) and using a jack-knife estimate of the variance will be used to assess the effect of the intervention on the primary and secondary outcomes above, depending on the type of outcome (e.g. count or proportion). This approach will account for the correlation between subjects in the same cluster, and for varying cluster sizes. Using an identity link (rather than a logit link) will allow us to estimate risk differences for binary outcomes.

Population averaged models estimated via GEE are robust to mis-specification of the correlation structure. While our data will surely have clustering at the household level as well, we need only account for the top-level cluster (here centre) and use the empirical standard errors to ensure that our inferences are conservative.

For count type outcomes, we will use a similar approach as described above, but using a Poisson distribution.

In secondary analyses, we will use logistic regression with a logit link estimated via GEE and also adjust for additional confounders (country, age, sex and smear status of index case). In sensitivity analyses we will analyze at the level of the cluster. Missing data will be dealt with via multiple imputation using chained equations which will allow us to impute binary as well as continuous variables .

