Third, we will estimate the cost-effectiveness of the streamlined intervention given to the former control sites in the secondary study. This will be estimated as the total research and health system costs for the Phase 1 and Phase 2 intervention package per added contact who starts LTBI therapy. This can also be compared to the cost-effectiveness (estimated in the same way) of the original intervention given to the original intervention sites.

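### The primary cost-effectiveness ratio uses a before-after change instead of the randomised difference and leaves out Phase 1 cost, so it is open to time trends and counts only part of the package cost

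*Protocol*

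**What the plan says.** Under the heading on estimation of costs and cost-effectiveness, the protocol fixes both parts of the ratio. For the numerator: "The primary cost-effectiveness measure will be the total cost of all Phase 2 activities", taken per additional contact who starts therapy. For the denominator: "Additional will be calculated based on the difference in proportion starting LTBI therapy between the pre- and post-intervention periods". The same section also states: "We will estimate the total Investigator, research staff, and clinic staff time involved in data gathering in Phase 1". That effort is therefore measured but not carried into the primary ratio.

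Other sections bear on this:

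- Rationale for study design describes what is being tested as "a standardized public health evaluation and analysis, with identification of problems (barriers), and appropriate solutions". The study hypothesis says the same in substance.
- Secondary objective 2 covers "the costs associated with the evaluation and implementation of appropriate solutions".
- Study Outcomes requires that index cases, contacts identified and contacts starting therapy "must be measured every month at all health facilities (Intervention and Control) throughout the trial".
- Data analysis for Phase 2 plans a between-arm GEE model: "Using an identity link (rather than a logit link) will allow us to estimate risk differences for binary outcomes". Count outcomes get a similar model with a Poisson distribution.
- The Data Analysis part of the cross-over study defines cost-effectiveness of the streamlined package as "total research and health system costs for the Phase 1 and Phase 2 intervention package per added contact who starts LTBI therapy", and adds that this can be compared with the original package estimated in the same way.

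**The concern.** There are three separate problems.

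**Effect.** The trial randomises clinics so that change over time can be separated from the effect of the package. The primary ratio does not use that contrast. A shift in starts that would have happened anyway, such as a policy change, drug supply or staffing, enters the denominator as if the package had produced it. The section also does not say which pre-intervention period is meant. It could be the retrospective cascade review, which is planned at intervention clinics, or the prospective monthly counts made before the solutions begin.

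**Cost.** The evaluation is half of what is being tested, and its cost falls under a stated objective. A ratio restricted to Phase 2 does not price the package that a TB programme would have to adopt. The cross-over section does include Phase 1, so the protocol holds two cost definitions, and the one named primary is the narrower.

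**Scale.** Identifying more contacts is one of the package's possible targets (Site A in the section on selecting solutions). The protocol also warns that identification may be absent or poorly recorded at some facilities. If the number identified changes, a change in the proportion starting does not convert to a number of additional starts.

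At stake is the figure meant to support affordability and scale-up.

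**Working it through.** The protocol states no cost total, Phase 1 cost share or cost-effectiveness ratio, so there is no figure of its own to reproduce. The check sets the definitions against each other and shows how far the ratio can move.

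**Inputs**

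- d, the randomised difference in proportion starting: 0.10. This is the protocol's own detectable difference from a 10% baseline at an ICC of 5% (Sample size considerations). As a plausibility check, the usual two-proportion formula for 0.10 versus 0.20 gives 199 per arm; 199 × 6.0 = 1194, against 1214 in Table 2.
- c, the change in the control arm over the same period: not given. Assumed range -5 to +10 points.
- s, the Phase 1 share of Phase 1 plus Phase 2 package cost: not given. Assumed range 0 to 50%.

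**Formula.** Assume equal baselines in the two arms and a fixed number of identified contacts. The before-after change at intervention clinics is then d + c, while the randomised difference is d. With package cost scaled to 1, the reported ratio is proportional to (1 - s)/(d + c) and the full randomised ratio to 1/d. Hence

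reported / full = (1 - s) × d / (d + c).

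Example: s = 0.20, c = +0.05 gives 0.80 × 0.10/0.15 = 0.53.

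| Control change c | s = 0 | s = 10% | s = 20% | s = 30% | s = 50% |
|---|---|---|---|---|---|
| -5 points | 2.00 | 1.80 | 1.60 | 1.40 | 1.00 |
| -2 points | 1.25 | 1.13 | 1.00 | 0.88 | 0.63 |
| 0 | 1.00 | 0.90 | 0.80 | 0.70 | 0.50 |
| +2 points | 0.83 | 0.75 | 0.67 | 0.58 | 0.42 |
| +5 points | 0.67 | 0.60 | 0.53 | 0.47 | 0.33 |
| +10 points | 0.50 | 0.45 | 0.40 | 0.35 | 0.25 |

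Values below 1 make the package look cheaper per additional start than it is; values above 1 make it look dearer. The row c = 0 isolates the Phase 1 omission, which always lowers the ratio by exactly s. The column s = 0 isolates the before-after choice, which works in either direction. The table leaves aside the between-arm difference in routine health-system cost, for which the protocol gives nothing to work with.

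**Scale, assumed figures.** Take the same number of index cases in both periods. Before: 100 contacts identified, 30 start (30%). After: 400 identified, 120 start (30%). The difference in proportions is 0, yet 120 - 30 = 90 more contacts start. The plan's denominator would be zero. This problem can work against the package.

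**The case against.** A reader might infer that the ratio overstates value for money, that both choices favour the intervention, and that a corrected ratio must look worse. The documents do not support this. Only the Phase 1 omission has a fixed direction. The section on LTBI activities at control sites has investigators facilitating access to materials and basic skills there, so some rise in controls is plausible. But it gives no timing and leaves the main responsibility with local programmes. If the help comes at the outset, it lifts the control baseline and creates no later trend. A 2-point fall in controls would cancel a 20% Phase 1 share, and a 5-point fall would reverse the net effect.

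A reader might also infer that the comparison of the original and streamlined packages is not like with like. The cross-over section says otherwise: both would be costed in the same way, on Phase 1 plus Phase 2. That part of the plan is sound. It can fairly be argued that a second measure is not in itself a contradiction, and that Phase 1 effort is collected and estimated, so readers are not denied it. What remains is that the measure named primary omits a component which the hypothesis, the rationale and secondary objective 2 all include.

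A before-after effect is also unavoidable in the cross-over. The comparison clinics there are former intervention clinics, so no untreated randomised comparator exists. This limits the fix but does not justify a before-after effect in the main trial, where such a comparator does exist.

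The cost section also mentions incremental health-system costs per additional contact. It names no control comparator for them, and additional starts have already been defined there as before versus after.

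**Conclusion.** The point stands in this form: the primary ratio is open to time trends, omits part of the package cost and rests on a denominator that does not give a number of starts. Taken alone, the Phase 1 omission understates package cost by the Phase 1 share, whatever that proves to be. Taken alone, at a true difference of 10 points, the before-after choice gives 0.83 to 0.50 of the randomised ratio if controls rise by 2 to 10 points, and 1.25 to 2.00 times it if they fall by 2 to 5 points. These sizes rest on assumed control trends and cost shares, equal baselines and a constant number of identified contacts. The net direction is not fixed by the documents. The two cost definitions differ and must be reconciled. The matter is confined to the cost-effectiveness objective and does not touch the primary effectiveness analysis. It should be corrected before the economic analysis is run.

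**What to change.** In the section on estimation of costs and cost-effectiveness:

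1. Define the incremental effect for the main trial as the randomised between-arm difference in months 13-18. Express it as starts per index case from a between-arm count model, the Poisson GEE already planned for counts, with index cases as the denominator. The primary outcome model does not yield this quantity, because its denominator is identified contacts.
2. Define the incremental cost as Phase 1 plus Phase 2 package cost plus the between-arm difference in health-system cost.
3. Use the same Phase 1 plus Phase 2 cost definition here and in the cross-over study's Data Analysis section.
4. Keep the before-after effect only for the streamlined package and for its comparison with the original package, labelled as non-randomised.

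The cost is rewording. Monthly counts of index cases and starts are planned at all clinics, research staff keep monthly activity logs covering Phase 1 and Phase 2, and time-and-motion measurements are planned twice at control clinics. Interval methods and any separation of pure research cost can be left to the analysis plan.

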### **Ascertainment of study outcomes - at all sites:**

Ultimately, in the intervention sites we will be able to use the newly developed and introduced Contact Management Registries (see below) to extract all necessary information and outcomes – including number of pulmonary TB cases (Index cases), number of contacts identified, and number who initiate LTBI therapy. However, these detailed contact registries are considered an integral part of the public health intervention, since considerable training in recording and reporting as well as the procedures of contact management will be needed for these to be completed accurately and completely. Introduction of these registries at control sites would be difficult without extensive training; if such training was given at the control sites, this would constitute a partial intervention, and reduce potential differences between intervention and control sites.

Hence recording of outcomes at control and intervention sites must rely on simple measures that can be implemented with minimal training, prior to the start of the trial at all sites. It is important that the procedures to ascertain (measure) these outcomes be established at the beginning of Phase 1, and continue **unchanged** at all health facilities (both intervention and control facilities) through-out the 18 months of the study.

Identification of contacts may not be performed, or not clearly recorded at all health facilities – especially the control facilities. This is why we must carefully document the number of index patients with active pulmonary TB diagnosed at each site. When the study is completed, the coordinating centre may use the number of index cases to estimate the number of household contacts that likely could have been identified (see Analysis section) Data sources will vary by site, depending what methods of documentation are already being used. We will collect information on the number of newly diagnosed index cases from lab or other sources that report active cases. The number of household contacts indentified will come from different sources depending on what is available the site. Finally, we will estimate the number of contacts who start LTBI treatment from hospital and or clinic records using a standard data collection form in all sites. The number of contacts completing LTBI therapy will be estimated retrospectively from clinic records.

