#### **Sample size considerations:**

As seen in Table 1 above (Study population), we estimate that during the 18 months of the study, 2475 active TB cases will be diagnosed at the participating sites, and 10,425 contacts will be identified, of whom 4975 will be diagnosed with LTBI. We wish to detect a 15% increase in the proportion of contacts that initiate therapy, with a level of statistical significance of 0.05 (alpha error). The intra-class correlation coefficient (ICC) which describes the inter-cluster heterogeneity, (or analogously the correlation amongst subjects in the same cluster) has less effect, but to be conservative we will assume this to be 0.05 to 0.1– which is high. In data from the 9INH vs 4RIF trial (comprising 6031 adults treated for latent TB in 12 centres), the ICC for the centre effect was low – just 0.01-0.02, depending on the method used to estimate it, for treatment completion. We will have 24 clusters in 5 countries. Our power calculations are based on the number of close contacts identified per randomization unit (from Table 1).

**Table 2: Detectable differences with all sites in all countries** (alpha=.05, and Power = 80%)

Proportion starting LTBI therapy in Control Arms	N Contacts per clinic	Design Effect	Total sample size per arm	Intra-Class Correlation	Detectable difference
0.10	100	2.0	1222	0.01	0.05
0.10	100	6.0	1214	0.05	0.10
0.10	100	10.9	1199	0.10	0.14
0.30	100	2.0	1236	0.01	0.08
0.30	100	6.0	1261	0.05	0.13
0.30	100	10.9	1221	0.10	0.18

Therefore, given 24 clusters in 5 countries, with at least 100 contacts per site every 6 months (based on minimum 40 active cases every year, and estimated 4.2 contacts per index case), and assuming that at baseline only 10% of contacts are started on Latent TB therapy, plus an ICC of 5%, we would have 80% power to detect a 10% increase in proportion of contacts starting therapy. If the number of contacts per site is higher this will actually have a modest effect on the detectable difference. If the proportion starting therapy is much higher (30%), then the detectable difference would be near 13%.

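### The cost-per-completion ratio omits the word 'additional'; read literally, it divides an incremental cost by all completers and understates the cost of each completion gained

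*Protocol*

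**What the plan says.** The Protocol section 'Estimation of costs, and cost-effectiveness' lists three ratios in one sentence. It begins "Incremental health system costs will be expressed per additional contact initiating LTBI (primary outcome" and continues "per additional active TB case detected, and per contact completing LTBI therapy (secondary outcomes) as measures of cost-effectiveness". The numerator is the same throughout. The denominators for starting treatment and for detecting active TB carry the qualifier *additional*; the denominator for completing treatment does not.

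Earlier in the same section the primary cost-effectiveness measure is also set per additional contact starting, and the term is defined: "Additional will be calculated based on the difference in proportion starting LTBI therapy between the pre- and post-intervention periods". The data analysis section of the cross-over study likewise sets its ratio per added contact who starts. No section says what an additional completer would be.

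On data, 'Ascertainment of study outcomes - at all sites' says: "The number of contacts completing LTBI therapy will be estimated retrospectively from clinic records".

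**The concern.** An incremental cost divided by a total count is neither an average cost nor an incremental cost-effectiveness ratio. It credits the package with contacts who would have completed anyway. The flaw shows without any assumption about effect size: if the package produced no extra completions, the cost per completion gained would be undefined, yet this ratio would still return a finite and apparently reasonable figure.

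The measure is secondary, but readers will look at it. The Protocol's rationale for the study design says that completion is needed for the long-term individual and public health benefit, and cost-effectiveness is a secondary objective. For a given absolute gain, the distortion grows with the baseline level. The sample-size section expects baselines to differ widely between countries, so literal ratios could not be compared fairly across countries, nor with the ratio per additional contact initiating in the same sentence.

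**Working it through.** **Inputs (Protocol, 'Sample size considerations')**
- Low baseline: "assuming that at baseline only 10% of contacts are started on Latent TB therapy", so p0 = 0.10.
- Gain from that baseline: "we would have 80% power to detect a 10% increase in proportion of contacts starting therapy", so p1 = 0.20 (ICC 0.05).
- Target: "We wish to detect a 15% increase in the proportion of contacts that initiate therapy". Read as 15 percentage points and applied to the 10% baseline, p1 = 0.25.
- High baseline: "If the proportion starting therapy is much higher (30%), then the detectable difference would be near 13" percentage points, so p0 = 0.30 and p1 = 0.43 (ICC 0.05).
- Planning ICC: 0.05 to 0.10. Canada (Table 3): p0 = 0.30, with gains of 0.27 to 0.29 at ICC 0.05 and 0.36 to 0.37 at ICC 0.10.
- Completion among starters: no planning value. The background cites a literature range of 20% to 80%.

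**Check of the planning scenarios.** The protocol states no cost-effectiveness figure to reproduce, so Table 2, which supplies the scenarios, was checked. The calculation was the usual two-proportion sample size (two-sided 0.05, power 80%, no continuity correction) multiplied by 1 + 99 × ICC:
- 10% to 20%, ICC 0.05: 199 × 5.95 = 1184 (stated 1214)
- 10% to 24%, ICC 0.10: 112 × 10.9 = 1221 (stated 1199)
- 30% to 43%, ICC 0.05: 215 × 5.95 = 1279 (stated 1261)
- 30% to 48%, ICC 0.10: 115 × 10.9 = 1254 (stated 1221)

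All four agree within 3%. In the two ICC 0.01 rows, solving at the stated sample size gives differences of 0.053 and 0.075, matching the printed 0.05 and 0.08 after rounding.

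**Formula.** Let c0 and c1 be completion among starters without and with the package, on a common number of contacts. All completers are proportional to p1·c1, and additional completers to p1·c1 − p0·c0. The literal ratio divided by the incremental ratio is (p1·c1 − p0·c0)/(p1·c1), so

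understatement = p0·c0 / (p1·c1).

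If c0 = c1, completion cancels at any value and the understatement is p0/p1. On raw counts or per index case, if contacts identified grow by a factor k, it becomes p0·c0 / (k·p1·c1).

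**Results**

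| Starting, p0 to p1 | c0 = c1 | c 50% to 60% | c 60% to 50% | c0 = c1, contacts doubled |
|---|---|---|---|---|
| 10% to 25% | 0.10/0.25 = 40% | 0.05/0.15 = 33% | 0.06/0.125 = 48% | 0.10/0.50 = 20% |
| 10% to 20% | 0.10/0.20 = 50% | 0.05/0.12 = 42% | 0.06/0.10 = 60% | 0.10/0.40 = 25% |
| 30% to 43% | 0.30/0.43 = 70% | 0.15/0.258 = 58% | 0.18/0.215 = 84% | 0.30/0.86 = 35% |

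The other combinations within the planned ICC range fall inside 40% to 70%: 0.10/0.24 = 42%, 0.30/0.48 = 62.5%, and 30% plus the 15-point target, 0.30/0.45 = 67%. The Table 2 rows at ICC 0.01, outside the planned range, give 0.10/0.15 = 67% and 0.30/0.38 = 79%.

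Canada, equal completion: 0.30/0.57 = 53% to 0.30/0.59 = 51% at ICC 0.05; 0.30/0.66 and 0.30/0.67, both about 45%, at ICC 0.10.

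With equal completion and equal contacts, the cost per additional completer is p1/(p1 − p0) times the literal ratio: 0.25/0.15 = 1.67 to 0.43/0.13 = 3.3.

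**The case against.** The strongest reply is that this is one dropped adjective. The sentence opens with incremental costs, two of its three items are explicitly incremental, and so are the primary cost-effectiveness measure and the cross-over ratio. No formula says that all completers are to be counted, and a statistical analysis plan, not shown here, may settle it. This stands as an explanation of how the wording arose: a reader should not infer that the investigators have decided to divide by all completers. It does not remove the point. The completion item restarts with its own preposition, so the qualifier does not carry over, and an analyst following the sentence would compute the wrong quantity.

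A reader might also take 40% to 70% as an unconditional result at the protocol's planning values. The documents do not support that. There is no planning value for completion, and the starting gains are detectable differences, not expected effects. Equal completion has some support, because no solutions are aimed at completion, but the protocol makes it a focus if it falls below 50%, and improving it is a secondary objective. The package may also increase the number of contacts identified, which lowers the figure on raw counts or per index case.

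Finally, a reader might attach the 70% to Canada because its assumed baseline is 30%. That figure uses the all-country 13-point difference; Canada's own table gives 45% to 53% over the planned ICC range, close to the 50% for the 10% to 20% scenario.

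**Conclusion.** The point holds as a wording error with a known direction. Read literally, the ratio understates the cost per completion gained whenever some contacts would complete without the package and the package adds completions. Its size is conditional: 40% to 70% at the sample-size scenarios requires equal completion among starters and equal contact numbers. The other columns of the table show how far it moves when either assumption fails. The primary outcome, the sample size, the primary cost-effectiveness measure and the cross-over ratio are untouched.

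**What to change.** In the sentence on incremental health system costs, write 'per additional contact completing LTBI therapy'. Define *additional* by the same comparison, base and period as the ratio per additional contact initiating. The section currently uses a difference in proportions between the pre- and post-intervention periods. Whichever comparison is kept there, the completion ratio must follow it; a different comparison or base, such as intervention minus control per index case for completion alone, would leave the two ratios not comparable. If an average cost per completer is also wanted, put total cost in the numerator and label it as an average.

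The cost is one sentence and its definition. Completion counts are already planned under the heading covering all sites. The downside is that the reported ratio becomes less favourable.
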